Malnutrition is common among cancer patients, with prevalence rates ranging from 16–40% at diagnosis and increasing to 40–80% during treatment, depending on factors such as age, cancer type, and treatment modality(Bossi *et al*, 2021; Kaegi-Braun *et al*, 2021). Tumor location plays a crucial role, with the highest malnutrition rates observed in pancreatic (66.7%), esophageal/gastric (60.2%), head and neck (48.9%), and lung (45.3%) cancers(Hébuterne *et al*, 2014; Bossi *et al*, 2021).

Nutritional status in cancer patients is intricately linked to clinical outcomes. Tumor and therapeutic interventions notably impact nutritional health(Webb *et al*, 2020; Kipouros *et al*, 2023). Malnutrition significantly affects treatment tolerance, morbidity, survival, and quality of life(Hébuterne *et al*, 2014; Liu *et al*, 2021; Garutti *et al*, 2023). It can lead to reduced nutrient intake, cachexia, and impaired treatment efficacy(Muscaritoli *et al*, 2019; Holdoway *et al*, 2023). Early nutritional interventions have been shown to mitigate adverse clinical outcomes and reduce 30-day mortality in at-risk patients(Muscaritoli *et al*, 2019; Schuetz *et al*, 2019; Kipouros *et al*, 2023).

Although the association between malnutrition and adverse clinical outcomes has been well established (Muscaritoli *et al*, 2019; Liu *et al*, 2021; Kipouros *et al*, 2023), the benefits of nutritional improvement reported in different studies remain inconsistent (Schuetz *et al*, 2019; Kaegi-Braun *et al*, 2021). On the one hand, nutritional status might vary considerably over the course of treatment(Webb *et al*, 2020); on the other hand, psychological factors, sleep quality, and physical activity may further influence these outcomes (Nissim *et al*, 2024; Ye *et al*, 2024). High-quality and large-scale cohort studies that can capture dynamic changes in nutrition are needed to carry out more precise nutritional interventions or treatments to improve clinical outcomes. Hence, we established a cohort study to evaluate nutritional status and clinical outcomes in patients with common malignancies (NCOM study), aiming to provide evidence for personalized and precise nutritional treatment in oncology care.

53 **Methods**

54 **Study design**

55 The NCOM study is a multicenter, prospective cohort study designed to assess longitudinal
56 changes in nutritional status and their impact on clinical outcomes in cancer patients. We aim

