57 primarily to identify modifiable risk factors associated with malnutrition-related morbidity and
58 mortality and assess the effectiveness of targeted nutritional interventions. The secondary objectives
59 include examining variations in nutritional status across cancer types and treatment modalities and
60 exploring how nutritional health interacts with psychological well-being, sleep quality, and physical
61 activity. Participants diagnosed with common malignancies across multiple hospitals undergo
62 baseline nutritional assessments within 48 hours of admission, followed by structured follow-ups at
63 1, 2, 3, 6, and 12 months and then annually for an additional four years to track nutritional changes
64 and key clinical endpoints (Riboli, 2001). Nutritional status, the primary exposure factor, is
65 classified via validated screening tools and dietary intake assessments. Patients are stratified on the
66 basis of malnutrition severity, dietary intake, and nutritional support status, with classifications
67 updated at each follow-up, to evaluate their associations with short- and long-term outcomes (**Fig.**
68 **1**).

[figure not shown]

Fig. 1. The workflow of the NCOM study.

Study Setting & Population

Study sites

The NCOM study was conducted across 11 tertiary hospitals in Xi'an, Shaanxi Province, China.

The participating institutions included Shaanxi Provincial Cancer Hospital; the First Affiliated

Hospital of Xi'an Jiaotong University; the Second Affiliated Hospital of Xi'an Jiaotong University; Shaanxi Provincial People's Hospital; the First Affiliated Hospital of the Fourth Military Medical University; the Second Affiliated Hospital of the Fourth Military Medical University; Shaanxi Provincial Chest Hospital; and the Affiliated Hospital of Northwest University Xi'an No.3 Hospital; Xi'an International Medical Center Hospital; The First Affiliated Hospital of Xi'an Medical University; The Second Affiliated Hospital of Xi'an Medical University.

Recruitment strategy

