Eligible patients will be recruited by clinical medical staff. Recruitment will primarily occur through direct physician referrals during oncology consultations, supplemented by promotional materials in hospitals, such as posters, brochures, and electronic notices. Patients and their families who learn about the study through these materials can also self-refer by contacting the research team. The screening process consists of two steps. The first screening visit (SV1) is conducted remotely via online consultation or phone call to assess basic eligibility, including willingness to participate and key exclusion factors such as pregnancy or concurrent trial participation. Informed consent is obtained at this stage. Patients who pass SV1 will proceed to the second screening visit (SV2), which will be conducted onsite at each hospital. During SV2, medical records will be reviewed, and clinical assessments will be performed to confirm whether patients meet the inclusion and exclusion criteria. Only patients who meet all the criteria will be formally enrolled.

Inclusion criteria

- a. Age \geq 18 years.
- b. Histologically confirmed diagnosis of malignancy.
- c. Patients are scheduled to receive oncologic treatment, including surgery, chemotherapy, radiotherapy, or a combination.
- d. Mentally competent and able to provide informed consent.
- e. Willingness to participate in follow-up assessments
- f. Patients with multiple hospital admissions may be included in repeat assessments, with each admission counted as an independent case.

Exclusion criteria

Patients were excluded if they met any of the following criteria:

- a. Severe comorbidities that may interfere with participation (e.g., end-stage liver/kidney disease or severe cardiac failure).
- b. Patients with HIV/AIDS.
- c. Prior organ transplantation recipients.
- d. Expected survival of less than 6 months.
- e. Pregnant patients.
- f. Patients currently participating in another interventional clinical trial.

Sample size

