Upon enrollment, trained personnel will obtain informed consent and record demographic details, including sex, age, marital status, occupation, education, and socioeconomic status. Lifestyle factors such as smoking, alcohol, and tea consumption are documented, given their potential influence on nutritional status and cancer progression(Yuan *et al*, 2023). Medical history, including chronic conditions, previous diagnoses, medication use, and family history of malignancies, will also be recorded to assess genetic predispositions.

Cancer-specific data will be collected at baseline and updated at follow-ups to monitor disease progression and treatment response. This includes pathology-confirmed diagnosis, TNM staging at first diagnosis, and available molecular markers. The tumor burden will be reassessed at each visit, alongside major treatments (surgery, chemotherapy, radiotherapy, targeted therapy, and immunotherapy), with details on the type, duration, and response. Nutritional support, including enteral or parenteral nutrition in the preceding week, will be tracked to evaluate its impact on treatment outcomes.

Karnofsky Performance Status (KPS): The KPS evaluates a patient's ability to perform daily activities, the presence of physical discomfort, and overall performance status, providing a standardized measure of functional impairment(McNair *et al*, 2023).

Nutritional assessments

Nutritional assessments will be conducted via validated screening tools to evaluate nutritional status, risk factors, and dietary intake patterns. Two primary tools and standardized anthropometric

measurements will be employed to assess malnutrition risk and severity:

Subjective Global Assessment (mPG-SGA): The mPG-SGA scoring system consists of five sections: weight loss history, dietary intake changes, symptoms, activity and function levels, and age. Patients' nutritional status will be categorized on the basis of scores as normal (0–2 points), mild malnutrition (3–6 points), and moderate malnutrition (≥ 7 points)(Huo *et al*, 2023a). The version used in this study, mPG-SGAL11, is an adapted and validated version developed for Chinese cancer patients who that incorporates modifications on the basis of nationwide clinical feedback and statistical validation(Fu *et al*, 2022; Huo *et al*, 2023b).

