Nutrition support in and out of hospital Nutrition support	√	√	√	√	√	√	√
Laboratory biomarkers	√	√	√	√	√	√	√
EORTC QLQ-C30	√	√	√	√	√	√	√
HADS	√	√	√	√	√	√	√
PSQI	√	√	√	√	√	√	√
Leisure-time physical activity levels	√	√	√	√	√	√	√
KAP Questionnaire	√				√	√	√
Short-Term Clinical Outcome		√	√	√	√	√	√
Long-term clinical outcomes		√	√	√	√	√	√
Adverse Event Recording	√	√	√	√	√	√	√

299 **Table 1.** Follow-up schedule. SV: screening visit; KPS: Karnofsky Performance Status; mPG-SGA:
 300 Subjective Global Assessment; NRS-2002: Nutritional Risk Screening 2002; SDSAT: Simple Diet Self-
 301 Assessment Tool; EORTC QLQ-C30: European Organization for Research and Treatment of Cancer

Quality of Life Questionnaire C30; HADS: Hospital Anxiety and Depression Scale; PSQI: Pittsburgh Sleep Quality Index; KAP : Knowledge, Attitude, and Practice.

Statistical analysis plan

Baseline characteristics are summarized as the means \pm standard deviations (SDs) for normally distributed variables, medians with interquartile ranges (IQRs) for skewed data, and percentages for categorical variables. For group comparisons (e.g., normal vs. mild malnutrition vs. moderate malnutrition patients), independent t tests or Mann–Whitney U tests were used for continuous variables, and chi–square tests or Fisher’s exact tests were used for categorical data.

The primary outcome analysis will apply multivariate regression models, adjusting for age, sex, cancer stage, treatment modality, socioeconomic status, and baseline Karnofsky Performance Status (KPS). Logistic regression was used to assess binary outcomes (e.g., nutritional risk, survival), whereas linear regression was used to evaluate continuous variables (e.g., BMI changes, weight loss percentage). To account for repeated measures, generalized estimating equations (GEEs) model longitudinal variations in nutritional status, biomarkers, and quality of life.

For survival analysis, Kaplan–Meier curves were used to estimate overall survival (OS) and progression-free survival (PFS), with log-rank tests used to compare groups. Cox proportional hazards models were used to explore the associations between nutritional status and survival outcomes, incorporating time-dependent covariates where applicable.

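### Entry is not limited to newly diagnosed or untreated patients, and the named covariates and subgroups omit disease phase at entry, a likely confounder of nutrition and survival

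*Protocol*

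**What the plan says.** **Who enters.** Under Inclusion criteria, (b) asks for "Histologically confirmed diagnosis of malignancy" and (c) states "Patients are scheduled to receive oncologic treatment, including surgery, chemotherapy, radiotherapy, or a combination". Criterion (f) adds: "Patients with multiple hospital admissions may be included in repeat assessments, with each admission counted as an independent case". No criterion requires a new diagnosis or first treatment, or limits time since diagnosis. The only exclusion framed in terms of prognosis is (d), "Expected survival of less than 6 months".

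**Time zero.** Study design anchors the start of follow-up to an admission: "baseline nutritional assessments within 48 hours of admission". It is not anchored to diagnosis or to the start of treatment.

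**Exposure and phase.** Nutritional status is the primary exposure. The Introduction gives "prevalence rates ranging from 16–40% at diagnosis and increasing to 40–80% during treatment", and says that these rates also depend on age, cancer type and treatment modality.

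**Data.** Demographics & Clinical Data lists "TNM staging at first diagnosis". It also lists previous diagnoses, tumor burden at each visit, and the type, duration and response of the major treatments.

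**Analysis.** The protocol's own Statistical analysis plan section specifies regression "adjusting for age, sex, cancer stage, treatment modality, socioeconomic status, and baseline Karnofsky Performance Status". Subgroups are cancer type, treatment modality and nutritional status category. Propensity score matching is planned without named covariates, and the Cox models may use time-dependent covariates where applicable.

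**The concern.** Phase at entry (untreated, on first-course treatment, or relapsed, progressed or on a later line) meets the usual description of a confounder. By the protocol's own figures it goes with the exposure, and it can be expected to go with survival and progression. If malnourished patients are more often already treated or relapsed, part of any association between malnutrition and mortality reflects where patients stand in their disease. Malnutrition-related mortality belongs to the primary aim.

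The named covariates only partly stand in for phase. Modality says which treatment is given, not whether it is the first course or a later line. The only stage named for collection is the one at first diagnosis. For a newly diagnosed patient that is current, but for a relapsed patient it may be out of date.

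A second consequence concerns trajectories. The Introduction motivates the study by changes in nutrition over the course of treatment. Visits at months 1, 2 and 3 counted from an arbitrary admission fall at different treatment points for different patients, so a pooled trajectory mixes them. The documents give no figure that would size this effect.

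**Working it through.** **Step 1. Can both phases enter?** Criterion (c) alone could be read as pre-treatment. Criterion (f) goes further: a patient's later admission may be included as its own case, and by then that patient may well be under treatment. Neither (b) nor any exclusion removes prior treatment or relapse. Both phases can enter, each with a new baseline.

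**Step 2. How far apart are the prevalences?** Ratio of during treatment to at diagnosis:
- low ends: 40/16 = 2.5
- midpoints: (40+80)/2 = 60 and (16+40)/2 = 28, so 60/28 = 2.14
- high ends: 80/40 = 2.0

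This is about twofold when like ends are paired. The two ranges touch at 40%, where the ratio would be 1.0.

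**Step 3. Unadjusted illustration with no nutrition effect in either phase.**

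Inputs from the Introduction: prevalence p0 at diagnosis and p1 during treatment. Assumed, because the protocol gives neither: the share f of patients in the treated phase at entry, and the hazard ratio h of treated versus untreated phase.

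- Treated share among malnourished: m = p1·f / [p1·f + p0·(1−f)]
- Treated share among well nourished: w = (1−p1)·f / [(1−p1)·f + (1−p0)·(1−f)]
- Approximate spurious hazard ratio: [1 + m(h−1)] / [1 + w(h−1)], the ratio of average hazards at the start of follow-up

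At the midpoints with f = 0.5:
- m = 0.60×0.5 / (0.60×0.5 + 0.28×0.5) = 0.682
- w = 0.40×0.5 / (0.40×0.5 + 0.72×0.5) = 0.357
- h = 1.5: 1.341/1.179 = 1.14
- h = 2: 1.682/1.357 = 1.24
- h = 3: 2.364/1.714 = 1.38

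**Step 4. Sensitivity to the assumptions.**

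| p0 / p1 | f | h = 1.5 | h = 2 | h = 3 |
|---|---|---|---|---|
| 16% / 40% | 0.3 | 1.13 | 1.23 | 1.38 |
| 16% / 40% | 0.5 | 1.12 | 1.21 | 1.32 |
| 16% / 40% | 0.7 | 1.09 | 1.14 | 1.20 |
| 28% / 60% | 0.3 | 1.13 | 1.24 | 1.41 |
| 28% / 60% | 0.5 | 1.14 | 1.24 | 1.38 |
| 28% / 60% | 0.7 | 1.11 | 1.17 | 1.25 |
| 40% / 80% | 0.3 | 1.16 | 1.30 | 1.54 |
| 40% / 80% | 0.5 | 1.19 | 1.33 | 1.56 |
| 40% / 80% | 0.7 | 1.16 | 1.27 | 1.41 |
| 40% / 40% | any | 1.00 | 1.00 | 1.00 |

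Pairing low with low and high with high, the range is 1.09 to 1.56. Opposite ends lie outside it: 40% in both phases gives 1.00, and 16% with 80% at f = 0.5 and h = 3 gives about 1.93. A weak phase effect (h = 1.25) gives only 1.05 to 1.10 over the same paired prevalences and treated shares.

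**Step 5. Scale.** The Sample size section states in words event rates of 20% and 24%, a risk ratio of 1.20. (Its bracketed rates differ, which is a separate matter.) With an overall event rate of 22%, a phase risk ratio of 2 and the midpoint case, the phase risks are 0.22/1.5 = 14.7% and 29.3%. The crude risks are then 14.7%×1.682 = 24.7% in malnourished and 14.7%×1.357 = 19.9% in well-nourished patients, a risk ratio of 1.24. Before adjustment, phase could thus produce a contrast about as large as the one stated in words.

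**The case against.** A reader might infer that nothing in the protocol separates the phases. The documents do not support that. Tumor burden, previous diagnoses and treatment type, duration and response are collected, so phase could largely be derived. KPS and modality are in the models and carry part of the phase information. The propensity covariates are open, and naming them may properly be left to a separate SAP. Excluding patients expected to survive less than 6 months also removes some of the late-phase patients with the worst prognosis and narrows the hazard contrast.

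A reader might also take the illustrative hazard ratios as the bias in the planned estimate. They are not. They are unadjusted, and they rest on an assumed phase mix and an assumed phase hazard. The prevalence contrast is not purely phase either: the protocol says that it varies with age, cancer type and modality, and age and modality are adjusted for. Finally, an admission-based cohort across cancers and treatments is a legitimate pragmatic design.

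All of this stands, and it limits the size of the concern. It does not close the gap. The protocol's own analysis section names its covariates and subgroups, and phase, prior treatment, recurrence and time since diagnosis are in neither list. Collecting related data does not commit the plan to using them.

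**Conclusion.** The point holds as a gap in design and adjustment. Eligibility mixes phases under one time zero, the protocol's own prevalence figures link phase to the primary exposure, and the named analysis does not commit to handling it.

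The size is not determined by the documents. With no nutrition effect and no adjustment, the spurious hazard ratio is about 1.14 to 1.38 in the midpoint 50:50 case for assumed phase hazard ratios of 1.5 to 3. It is 1.09 to 1.56 across the paired ends at treated shares of 30–70%, and nil if prevalence is 40% in both phases. After adjustment for KPS and modality it should be smaller, by an amount that cannot be calculated here. The documents do not show that the cohort is mostly pre-treated or that the final estimate will be materially biased. The change should be made because the confounder is foreseeable and cheap to handle.

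**What to change.** - At the index admission, record the date of first diagnosis and the phase at entry (untreated; on first-course treatment; relapsed, progressed or later line), or derive them from the medical records already reviewed at SV2.
- Add phase and time since diagnosis to the regression and propensity models, or stratify the Cox models by phase. Use phase at entry only: treatment given after baseline may lie on the causal path.
- Report the primary association and the nutritional trajectories in untreated patients as a sensitivity analysis.

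The cost is two baseline fields and some analysis wording, with no extra patients or procedures. The untreated stratum is smaller than the whole cohort, so its estimates will be less precise.

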The sample size for the NCOM study was determined on the basis of the impact of nutritional status on clinical outcomes in cancer patients, with a two-sided significance level (α) of 0.05 and 80% power ($1 - \beta = 0.80$) (von Elm *et al*, 2007; Arends *et al*, 2017). On the basis of previous studies on nutritional status and cancer outcomes, we assumed a baseline event rate of 20% ($P_1 = 0.50$) in the unexposed group and an expected rate of 24% ($P_2 = 0.40$) in the exposed group (Rasschaert *et al*, 2024). Given that longitudinal oncology cohort studies report attrition rates ranging from 30% to 50% over a multiyear follow-up period (Reeves *et al*, 2007; Schwedhelm *et al*, 2016), the final target sample size for this study was estimated to be approximately 1,538 participants.

Data collection

Data collection followed a standardized protocol across all participating hospitals to ensure consistency and accuracy. The baseline assessments will be conducted within 48 hours of hospital admission, and well-trained researchers will collect information on demographic and clinical data, nutritional status, laboratory biomarkers, quality of life, psychosocial factors, physical activity, sleep status, and knowledge, attitudes, and practices (KAPs). Follow-up assessments will be conducted at predefined intervals to track longitudinal changes in nutritional status and clinical outcomes.

To ensure data reliability, each hospital will designate 1 to 2 trained personnel to be responsible for questionnaires and clinical data recording. At the same time, a supervisor will be appointed to review the integrity of the data and coordinate follow-up work if necessary. All researcher personnel

must complete standardized training and pass competency assessments to ensure consistency in data collection and minimize variations.

Data management will be centralized through the Research Electronic Data Capture (REDCap) system, which ensures data security, accuracy, and accessibility(Harris *et al*, 2009). Standardized, validated measurement tools will be used at each site. Data entry will include built-in validation checks to identify missing values or inconsistencies, with routine audits and cross-site comparisons performed to maintain high data quality and study validity.

Data Content & Assessment Tools

Demographics & Clinical Data

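### Inclusion criterion (f) counts every admission of a patient as an independent case, against a target in participants and patient-level survival outcomes, with no patient-level clustering stated for the survival and binary analyses

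*Protocol*

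**What the plan says.** Four places in the protocol bear on the unit of analysis.

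- **Inclusion criteria, item (f):** "Patients with multiple hospital admissions may be included in repeat assessments, with each admission counted as an independent case".
- **Sample size:** "the final target sample size for this study was estimated to be approximately 1,538 participants". The unit is the participant, and no allowance for clustering is mentioned.
- **Short-Term & Long-Term Clinical Outcomes:** long-term follow-up classifies each patient by vital and disease status and records the cause of death. These are facts about a patient, not about an admission.
- **Statistical analysis plan:** survival is an example of a binary outcome for logistic regression. OS and PFS are analysed by Kaplan-Meier curves, log-rank tests and Cox models. The provision for repeated measures is: "To account for repeated measures, generalized estimating equations (GEEs) model longitudinal variations in nutritional status, biomarkers, and quality of life". Mixed-effects models are also named, for the psychosocial analyses. Neither provision extends to death, OS, PFS or the other binary outcomes.

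**The concern.** Two admissions of one patient are not independent, so the rule is wrong as worded. It is also a positive statement about the unit of analysis, not a detail left for a later SAP. A SAP that clustered by patient would have to depart from it.

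Three consequences follow if the rule is applied as written.

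- A patient enrolled at two admissions who later dies can contribute two deaths to analyses that treat rows as independent. Standard errors then come out too small, to a degree set by how strongly exposure and outcome are both correlated within a patient.
- Patients admitted often get more weight, so estimates describe admissions rather than patients.
- Recruitment could reach 1,538 cases with clearly fewer than 1,538 people, although the calculation behind that number assumes independent units.

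**Working it through.** **1. Reproducing the target.** The Sample size section states each event rate twice, with different values. For unexposed patients the text is "we assumed a baseline event rate of 20% ($P_1 = 0.50$) in the unexposed group". For exposed patients, where the same kind of mismatch occurs, it is "an expected rate of 24% ($P_2 = 0.40$) in the exposed group". That contradiction is a separate matter. I use 0.50 and 0.40 because only they reproduce the target. Other inputs from the section are two-sided alpha 0.05, 80% power, and "attrition rates ranging from 30% to 50% over a multiyear follow-up period". I assume equal groups and unpooled variance.

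- Per group: (1.96 + 0.8416)² × (0.50×0.50 + 0.40×0.60) / 0.10² = 7.849 × 0.49 / 0.01 = 384.6
- Both groups: 769.2
- With 50% attrition: 769.2 / (1 − 0.50) = 1,538.4

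The stated 1,538 is therefore 769 evaluable independent units with a design effect of 1. The worded rates of 20% and 24% would need 3,366 evaluable (pooled formula), or 4,809 to 6,732 after 30% to 50% attrition.

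**2. Unique patients if admissions fill the target.** At an average of m admissions per patient, the number of people is 1,538 / m: 1,025 at m = 1.5, 769 at m = 2, and 513 at m = 3.

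**3. Effect on the tests.** For a regression coefficient with m rows per patient, an approximate design effect is

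DE = 1 + (m − 1) × ρx × ρy,

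where ρx and ρy are the within-patient correlations of exposure and outcome. A model that ignores clustering understates the standard error by a factor 1/√DE. The true two-sided type I error of its nominal 5% test is 2 × [1 − Φ(1.96/√DE)]. The protocol gives none of m, ρx or ρy, so all three are assumptions.

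| m | ρx × ρy | DE | SE ratio | True type I error | Effective units of 769 | Power, 0.50 vs 0.40 |
|---|---|---|---|---|---|---|
| 2 | 0.25 (both 0.5) | 1.25 | 0.89 | 8% | 615 | 0.70 |
| 2 | 0.5 | 1.5 | 0.82 | 11% | 513 | 0.62 |
| 2 | 1 (both 1) | 2 | 0.71 | 17% | 384 | 0.50 |
| 3 | 1 (both 1) | 3 | 0.58 | 26% | 256 | 0.36 |

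The power column applies if the 769 evaluable rows are admissions and the test allows properly for clustering.

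**4. Simulation check.** I took 769 patients with no true effect, a varying (Poisson) number of readmissions, and one death status per patient copied to every admission. The correlation of the variable underlying exposure ran from 0.5 to 1.0. Each setting was fitted 1,000 times by logistic regression.

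| Mean admissions | Type I error, rows independent | Type I error, clustered by patient |
|---|---|---|
| 1.5 | 0.08 to 0.14 | about 0.05 |
| 2 | 0.11 to 0.22 | 0.04 to 0.06 |
| 3 | 0.16 to 0.32 | 0.04 to 0.05 |

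The upper values exceed the formula because admissions vary between patients. With mean 2 and variance 1, the relevant cluster size is (1 + 4)/2 = 2.5 rather than 2.

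**The case against.** The strongest defence is that criterion (f) is permissive and does not itself say that admissions are the rows of the survival models. Other text points to the patient: the target is in participants, survival status is the patient's, the Study design section updates classifications at each follow-up, and the Cox models allow time-dependent covariates. Row unit and variance estimator are often settled in a SAP. This shows that the protocol is inconsistent and that duplication is a risk rather than a certainty. It does not remove the independence clause, which is the only statement in the protocol on how repeat admissions count.

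Several stronger readings are tempting, and the document does not support them.

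- **Survival time is duplicated.** A reader might infer this, but if each entry's clock starts at its own admission, the times differ. The protocol states no time zero. What can be duplicated is the death.
- **OS and PFS outcomes are perfectly correlated within a patient.** A progression between two admissions is an event for the first entry only. Thirty-day outcomes need not be shared either: a patient readmitted after day 30 was alive at day 30 of the first stay.
- **Having to survive to readmission biases the results.** That depends on the unstated time zero. If each entry starts at its own admission, the argument falls away and only the extra weight remains.
- **Type I error will be 17% or 26%.** Those figures need constant exposure, a fully shared outcome, and two or three admissions for every patient. The Introduction itself says nutritional status can change a good deal during treatment. If few patients re-enter, the effect is small.

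**Conclusion.** The point stands as an error in the protocol. Criterion (f) fixes an independence that cannot hold, and it conflicts with a target in participants and with patient-level survival outcomes. The logistic, Kaplan-Meier, log-rank and Cox analyses state no within-patient correction that would absorb it. The planned GEE and mixed-effects models cover other outcomes.

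The size cannot be derived from the document. Under the stated assumptions, true type I error runs from about 8% (two admissions, both correlations 0.5) through 11% and 17% to 26% (three admissions, both correlations 1). It would be closer to 5% if readmission into the cohort is rare or exposure changes freely between admissions. The conflict between participants and cases, and the added weight of readmitted patients, do not depend on these correlations.

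**What to change.** - In inclusion criterion (f), delete the closing clause that makes each admission an independent case. State that only unique patients count towards the 1,538.
- Link a patient's admissions by a pseudonymous study ID across all 11 hospitals. The Data Privacy & Confidentiality section says personal identifiers are not recorded, so the link must be made during data collection; analysis cannot recreate it.
- For death, OS and PFS, choose one approach and state it. Either the first enrolled admission sets baseline and time zero, with later admissions as repeated or time-dependent measurements, or admissions remain as rows with patient-clustered robust variance or a frailty term. Both repair the standard errors. Under the second, time zero for each row must be defined and the extra weight of readmitted patients acknowledged.
- For per-admission outcomes (length of stay, cost, complications), use patient-clustered standard errors or a patient random effect.

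The text change is short, but it is not free. Confidence intervals widen. Parts of the protocol are in the past tense, so enrolment may have begun; if admissions have already been counted towards 1,538, the number of unique patients and the resulting power must be restated.

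### The sample size paragraph gives each group two different event rates; the target of 1,538 fits 50% vs 40% and cannot come from 20% vs 24%

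*Protocol*

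**What the plan says.** The Sample size section of the protocol sets a "two-sided significance level (α) of 0.05" and "80% power ($1 - \beta = 0.80". It then gives the planning rates: "a baseline event rate of 20% ($P_1 = 0.50$) in the unexposed group and an expected rate of 24% ($P_2 = 0.40", the second rate being for the exposed group. For loss to follow-up it cites "attrition rates ranging from 30% to 50% over a multiyear follow-up period", without naming the single value applied. It concludes that "the final target sample size for this study was estimated to be approximately 1,538 participants".

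The paragraph gives no ratio of exposed to unexposed patients, no formula, and no number needed before attrition. It does not say which event the rates describe or by what time. The section on short-term and long-term clinical outcomes lists several candidates (30-day survival status, ICU admission, complications, long-term survival and progression) and does not tie any of them to these rates.

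**The concern.** Each group has two planning rates in one sentence, and they cannot both be right. In words, the exposed group has 4 points more events than the unexposed group. In symbols, it has 10 points fewer. So the size of the effect and the sign of the hypothesis are both unclear.

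This matters because the paragraph is the protocol's only quantitative justification for the size of the cohort. A reader who takes the words at face value will believe that the study has 80% power for a difference of 4 points. If the number was derived from the other pair, that belief is wrong by a wide margin, and a non-significant result would say little about an effect of that size.

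**Working it through.** **Inputs from the Sample size section.** Two-sided α = 0.05 (z = 1.960); power 80% (z = 0.842); rates 0.20 vs 0.24 (words) or 0.50 vs 0.40 (symbols); attrition 30% to 50%; target 1,538.

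**Assumptions of this check.** Equal groups unless stated otherwise; enrolled = analysable / (1 − loss); each lost patient contributes nothing.

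**1. Reproducing 1,538 from the symbols.** Two proportions, unpooled variance:

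n per group = (1.960 + 0.842)² × [p₁(1−p₁) + p₂(1−p₂)] / (p₁−p₂)²

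= 7.849 × (0.25 + 0.24) / 0.10² = 384.6

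Total 769.2; at 50% loss 769.2 / 0.5 = 1,538.4. This matches the stated target. The pooled-variance formula gives 387.3 per group and 1,549 at 50% loss. With equal groups and the unpooled formula, 30% loss gives 1,099 and 40% loss gives 1,282, which do not match.

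**2. Other routes from the same pair.** Because the split and the attrition value are not stated, other combinations of 0.50 vs 0.40 also land near the target:

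| Exposed share | Loss | Variance | Enrolled |
|---|---|---|---|
| 50% | 50% | unpooled | 1,538 |
| 23% | 30% | unpooled | 1,534 |
| 30% | 40% | pooled | 1,540 |
| 29% | 40% | unpooled | 1,543 |

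**3. The same calculation from the words.** For 0.20 vs 0.24, unpooled: 7.849 × (0.16 + 0.1824) / 0.04² = 1,679.7 per group. Pooled: 1,682.4 per group, 3,365 in total. Enrolled: 3,365 / 0.7 = 4,807 at 30% loss and 3,365 / 0.5 = 6,730 at 50% loss. Continuity correction, a one-sided test, the arcsine formula and splits from 1:4 to 4:1 were also tried. The lowest total was 2,648 (one-sided, no loss), still far above 1,538.

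**4. Power of 1,538 enrolled for 20% vs 24%, equal groups.** Power = Φ[(0.04 − 1.960 × SE₀) / SE₁], with SE₀ = √(0.22 × 0.78 × 4/N) and SE₁ = √((0.16 + 0.1824) × 2/N).

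| Loss | Analysable N | SE₀ | SE₁ | Power |
|---|---|---|---|---|
| 50% | 769 | 0.02988 | 0.02984 | 26.7% |
| 40% | 923 | | | 31.1% |
| 30% | 1,077 | 0.02525 | 0.02522 | 35.3% |
| none | 1,538 | 0.02113 | 0.02110 | 47.3% |

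For comparison, 769 analysable patients give 79.7% power for 50% vs 40% by the same formula.

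**5. Detectable rate at 80% power from a 20% base, equal groups.** 28.7% at 50% loss and 27.2% at 30% loss.

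**The case against.** The strongest reply is that this is a typing error. The symbols reproduce the target to the digit, so the authors probably worked from 0.50 vs 0.40 and left wrong percentages in the sentence. If so, the number is sound under its assumptions and only the wording needs correction. That may well be right, but the protocol does not say so. The words are the part that most readers will take away, and no other section shows which pair was intended.

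The low power figures are also conditional. They apply only if 20% vs 24% was meant, and they assume equal groups and complete loss of 30% to 50% of patients. The analysis plan includes Cox models and multiple imputation, so patients with incomplete follow-up may still contribute. This stands as a limit on the 27% to 35% range. It does not rescue the 80%, because power is only 47% with nobody lost.

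Two stronger readings should be resisted. A reader might infer that 1,538 can arise only from equal groups with 50% attrition; step 2 shows other combinations that fit. A reader might also infer that the plan wrongly assumes half the cohort is exposed, since the Introduction gives malnutrition as 16% to 40% at diagnosis. The protocol states no split, so equal groups are a reconstruction. The Introduction's sentence in full reads "with prevalence rates ranging from 16–40% at diagnosis and increasing to 40–80% during treatment". Enrolment is not limited to newly diagnosed patients, and exposure is reclassified at each follow-up. A share near one half is therefore compatible with the protocol's own figures.

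**Conclusion.** The point stands as an error on the face of the text: two incompatible pairs of rates, opposite in direction, in the sentence on which the sample size rests. The target agrees with 0.50 vs 0.40 and with no tested variant of 20% vs 24%, which needs more than twice as many analysable patients as the whole planned enrolment (3,365 against 1,538).

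Whether the 80% power is false depends on which pair was meant. For 50% vs 40% it is about right under the simplest reconstruction. For 20% vs 24% it is wrong in every case examined: about 27% to 35% with equal groups and 50% to 30% loss, and 47% with no loss. The missing attrition value and exposed fraction prevent a reader from confirming the derivation. The unnamed event and time point prevent a check of either pair against an outcome.

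**What to change.** Rewrite the Sample size paragraph so that it:

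- keeps one pair of rates, corrects the other, and states whether exposure is expected to raise or lower the event rate;
- names the event and the time point to which the rates refer;
- states the attrition value, the exposed fraction and the formula used.

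If 20% vs 24% is meant, replace the 80% power statement with the actual power (about 27% to 35%, conditional on equal groups and 50% to 30% loss). Also give the difference that 1,538 enrolled can detect at 80% power: about 27% to 29% against 20%. If 50% vs 40% is meant, correct the percentages in words and state the assumptions that yield 1,538.

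The cost is one paragraph of protocol text. No extra enrolment is needed. Under the 20% vs 24% reading, the price is a less favourable power statement.
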